### 7.5.1 Routine Reporting of Adverse Events

All AEs, whether or not associated with the IMP that are observed by the Investigator, other Investigational Site personnel, or those reported by the subject will be recorded in the subject's source documentation and on the AE page of the eCRF. Copies of the SAE eCRF pages or an SAE listing generated based on the eCRF pages will be submitted to the Sponsor at regularly scheduled intervals to allow the Sponsor to meet expedited regulatory reporting requirements under 21 CFR 312.32 and regular regulatory reporting requirements under 21 CFR 312.33.

For each AE, the following information will be entered in the eCRF:

- Medical diagnosis of the event in standard medical terminology (if a medical diagnosis cannot be determined, a description of each sign or symptom characterizing the event);
- Date of onset of any new AE or worsening of a previously observed AE. For the days when the subject is in the clinic (Visit 2 to Visit 9), the time (based on a 24-hour clock) of onset should be recorded if available;
- Date of resolution of the event (or confirmation ongoing). For the days when the subject is in the clinic (Visit 2 to Visit 9), the time (based on a 24-hour clock) of resolution should be recorded if available;
- Whether the event is serious (per definition in [Section 7.4](#)), and if so, the reason it is considered serious;
- Severity of AE (per definition in [Section 7.7](#));
- Assessment of the attributability of the AE to the IMP [per definition in [Section 7.5](#)];
- Expectedness of AE (per definition in [Section 7.8](#));
- Action taken in treating the AE (including concomitant medications or therapies administered) and/or change in the IMP administration or dose (including whether the IMP was temporarily interrupted or discontinued);
- Outcome of AE (per definition in [Section 7.9](#)).

### 7.5.2 Reporting of Serious Adverse Events

In accordance with Federal regulations, Investigators will be notified of the occurrence of serious, unexpected and related adverse events.

The Investigator must report all serious adverse events to Sponsor or delegate within 24 hours of the site being notified of the event. Investigators must also report these events to the Institutional Review Board (IRB) in accordance with the IRB's reporting guidelines, within the IRB specified timeframe, or no later than 48 hours after knowledge of the event.

For submission of these events to the Israeli Regulatory Agency- the Sponsor will follow FDA regulations 21 CFR 312.32. If the event is determined to meet the requirements of IND Safety Reporting, then expedited reporting requirements to the FDA will be followed. The Sponsor may need to issue an Investigator notification, to inform all Investigators involved in any study with

the same drug (or therapy) that this serious unexpected suspected adverse reaction (SUSAR) has occurred.

#### Investigator Reporting Procedures

The PI or other study personnel must immediately (within 24 hours) inform Sponsor representative of any AE considered serious (as defined above) or otherwise medically significant. Notification should be via email or facsimile transmission of a written report signed by the PI. Notification must include the PI's assessment as to whether the event was or was not related to the use of the study medication.

#### 7.5.2.1 Pregnancy Reporting

If the subject or partner of a subject participating in the study becomes pregnant during the study or within 30 days of discontinuing study medication, the Investigator should report the pregnancy to Oramed within 24 hours of being notified. The Exposure In-Utero form to the Investigator for completion.

The subject or partner should be followed by the Investigator until completion of the pregnancy. If the pregnancy ends for any reason before the anticipated date, the Investigator should notify the Sponsor. At the completion of the pregnancy, the investigator will document the outcome of the pregnancy. If the outcome of the pregnancy meets the criteria for immediate classification as an SAE (i.e., postpartum complication, spontaneous abortion, stillbirth, neonatal death, or congenital anomaly), the Investigator should follow the procedures for reporting an SAE.

## 7.6 Causality Assessment of Adverse Events

For all AEs, the Principal Investigator will provide an assessment of causal relationship to the study medication. The causality assessment must be recorded in the subject's source documents and, on the AE eCRF. Causal relationship will be classified according to the following criteria:

1. *Unrelated*: The event is clearly due to causes other than the active study drug.
2. *Unlikely*: The event is doubtfully related to active study drug. The event was most likely related to other factors such as the patient's clinical state, concomitant drugs or other therapeutic interventions.

3. *Possible*: The event follows a reasonable temporal sequence from the time of active study drug administration but could have been produced by other factors such as the patient's clinical state, therapeutic interventions or concomitant drugs.
4. *Probable*: The event follows a reasonable temporal sequence from the time of active study drug administration and follows a known response pattern to the drug. The toxicity cannot be reasonably explained by other factors such as the patient's clinical state, therapeutic interventions or concomitant drugs.
5. *Definite*: The event follows a reasonable temporal sequence from the time of active study drug administration, follows a known response pattern to the drug, cannot be reasonably explained by other factors such as the patient's condition, concomitant drugs or therapeutic interventions, AND either occurs immediately following active study drug administration, improves on stopping the study drug, or reappears on re-exposure.

### 7.6.1 Potential Adverse Events Associated with ORMD-0801

Hypoglycemia and associated symptoms (e.g., weakness, dizziness, shakiness, increased sweating, palpitations, or confusion), have been associated with insulin administration, including ORMD-0801. Animal reproductive studies have not been conducted with ORMD-0801. It is not known whether ORMD-0801 can cause fetal harm when administered to a pregnant woman. It is also not known whether this product is excreted in human milk. Pregnant or breastfeeding women are excluded from this study.

Long-term animal studies have not been completed to assess whether ORMD-0801 impairs fertility.

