### 3.2.2 Screen Failure

A screen failure is defined as a subject who has signed the ICF, does not meet all the entry criteria outlined in [Section 4](#) of this protocol. Note that this includes assessments through Visit 1 (up to Days -42), prior to receiving IMP.

The Investigator is responsible for keeping a record of all subjects screened for entry into the study and subsequently excluded. The reason(s) for exclusion will be recorded in the source documents and on the Screening log.

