## 4 STUDY SUBJECT SELECTION

### 4.1 Inclusion Criteria

Each subject must meet all of the following criteria to be eligible for the study:

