#### Inclusion Criteria

1. Male or female aged 18-70 years.
2. BMI  $\geq 25$ .
3. Known type 2 DM according to American Diabetic Association (one of the three needed): Fasting Plasma Glucose  $\geq 126$  mg/dl or 2h postprandial (PG) following 75g OGTT  $\geq 200$  mg/dl or HbA1c  $> 6.5\%$  or on treatment with metformin only or metformin in addition to no more than two of the following medications sulfonylurea, DPP-4 inhibitors, GLP-1 receptor agonists, Thiazolidinediones (TZDs).
4. Diagnosis of NAFLD by non-invasive determination of hepatic steatosis grade S1, defined as hepatic steatosis  $> 8\%$ , by MRI- PDFF and CAP FibroScan  $\geq 238$  dB/m.
5. Liver enzyme abnormalities: ULN  $\leq 5$  times.
6. Fibrosis score  $1 \leq F \leq 3$  as defined by FibroScan measurement (Liver stiffness measurement, LSM) of  $6 \leq \text{LSM} \leq 12$  kPa.
7. Signature of the written informed consent.
8. Negative serum pregnancy test at study entry for females of childbearing potential.
9. Women of childbearing potential must have a negative urine pregnancy test result prior to the start of the run-in period and initiation if active dosing. Males and females of childbearing potential must use two methods of contraception (double barrier method), one of which must be an acceptable barrier method from the time of screening to the last study visit (22 weeks). Barrier methods of contraception include male condoms plus spermicide, diaphragm with spermicide plus male condom, and cervical cap with spermicide plus male condom. Acceptable methods of birth control include abstinence, oral contraceptives, surgical sterilization, vasectomy, the contraceptive patch, and the contraceptive ring. If a subject is not usually sexually active but becomes active, he or his partner should use medically accepted forms of contraception. Sperm donations will not be allowed for the duration of the study and for 90 days after the last dose of study drug.  
Females of non-childbearing potential are defined as postmenopausal who a) had more than 24 months since last menstrual cycle with menopausal levels of FSH (FSH Level  $> 40$ ), b) who are surgically menopausal (surgical sterility defined by tubal occlusion, bilateral oophorectomy, bilateral salpingectomy or hysterectomy).

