## 4.2 Exclusion Criteria

Subjects who meet any of the following criteria must be excluded from the study:

1. Patients with active (acute or chronic) liver disease other than NASH (e.g. viral hepatitis, genetic hemochromatosis, Wilson disease, alpha-1 antitrypsin deficiency, alcohol liver disease, drug induced liver disease) at the time of enrolment.
2. ALT or AST > 5 times ULN.
3. Abnormal synthetic liver function (serum albumin  $\leq$ 3.5gm%, INR >1.3).
4. Known alcohol and/or any other drug abuse or dependence in the last five years.
5. Weight >120 Kg (264.6 lbs.).
6. Known history or presence of clinically significant, cardiovascular, gastrointestinal, metabolic (other than diabetes mellitus), neurologic, pulmonary, endocrine, psychiatric, neoplastic disorder or nephrotic syndrome.
7. History or presence of any disease or condition known to interfere with the absorption, distribution, metabolism or excretion of drugs including bile salt metabolites (e.g. inflammatory bowel disease (IBD), previous intestinal (ileal or colonic) operation, chronic pancreatitis, celiac disease or previous vagotomy.
8. Weight loss of more than 5% within 6 months prior to enrolment.
9. History of bariatric surgery.
10. Uncontrolled blood pressure BP  $\geq$ 150/ $\geq$ 95.
11. Non type 2 DM (type 1, endocrinopathy, genetic syndromes etc.).
12. Patients with HIV.
13. Daily alcohol intake >20 g/day (2 units/day) for women and >30 g/day (3 units/day) for men.
14. Treatment with anti-diabetic medications other than metformin and more than-two of the following medications sulfonylurea, DPP-4 inhibitors, GLP-1 receptor agonists, TZDs
15. Metformin, fibrates, statins, not provided on a stable dose in the last 6 months.
16. Patients who are treated with valproic acid, Tamoxifen, methotrexate, amiodarone.
17. Chronic treatment with antibiotics (e.g. Rifaximin).
18. Homeopathic and/or Alternative treatments. Any treatment must be stopped before the screening period.
19. Uncontrolled hypothyroidism defined as Thyroid Stimulating Hormone >2X the upper limit of normal (ULN). Thyroid dysfunction controlled for at least 6 months prior to screening is permitted.
20. Patients with renal dysfunction: eGFR < 40 ml/min.
21. Unexplained serum creatinine phosphokinase (CPK) >3X the upper limit of normal (ULN). Patients with a reason for CPK elevation may have the measurement repeated prior to enrolment; a CPK retest > 3X ULN leads to exclusion.

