22. Subjects meeting criteria for contraindication for MRI – including the following:
  - History of severe claustrophobia impacting ability to perform MRI during the study, even despite mild sedation/treatment with an anxiolytic.
  - Subjects with metal implants, devices, paramagnetic objects contained within the body and excessive or metal containing tattoos.
  - Subjects unable to lie still within the environment of the MRI scanner or maintain a breath hold for the required period to acquire images, even despite mild sedation/treatment with an anxiolytic.

23. Subject participated in a clinical research study involving a new chemical entity within 4 weeks of study entry.
24. Known allergy to soy.

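### Section 7.6.1 says breastfeeding women are excluded, but no numbered eligibility criterion says so, so a site applying Section 4 can enrol them

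*Combined protocol and SAP*

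**What the plan says.** Section 7.6.1, on potential adverse events of ORMD-0801, states that "Pregnant or breastfeeding women are excluded from this study". Just before that it gives a reason for caution: "It is also not known whether this product is excreted in human milk".

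Eligibility is set in Section 4. Section 4.1 opens with "Each subject must meet all of the following criteria to be eligible for the study" and lists 12 items. Section 4.2 opens with "Subjects who meet any of the following criteria must be excluded from the study" and lists 24 items, the last of which is "Known allergy to soy". The synopsis repeats both lists.

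Pregnancy is handled by inclusion criterion 8 ("Negative serum pregnancy test at study entry for females of childbearing potential") and by inclusion criterion 9, which begins "Women of childbearing potential must have a negative urine pregnancy test result prior to the start of the run-in period" and goes on to contraception. Breastfeeding appears nowhere in the documents except Section 7.6.1.

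**The concern.** The risk section presents the exclusion of breastfeeding women as a settled feature of the trial, but the lists that sites use to decide who enters do not contain it. A reader of Section 7.6.1, including an IRB, would take the protection to be in place. A coordinator working through the criteria in Section 4 would find nothing to apply.

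What is at stake is a possible exposure that the protocol says it prevents. The trial enrols women from age 18 and treats for 12 weeks, and its primary objective is safety. Whether a nursing infant would in fact be exposed is not established, since the protocol says only that excretion in milk is unknown. That uncertainty is stated directly before the exclusion.

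**Working it through.** No figure in the plan depends on this point, so the check is a comparison of text. The question at each place is whether it would stop a breastfeeding woman from being enrolled or kept on treatment.

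| Place | Pregnancy | Breastfeeding |
|---|---|---|
| Section 7.6.1 | stated as excluded | stated as excluded |
| Section 4.1, 12 inclusion criteria | criteria 8 and 9 | not mentioned |
| Section 4.2, 24 exclusion criteria | not mentioned | not mentioned |
| Synopsis, same two lists | criteria 8 and 9 | not mentioned |
| Section 3.2.1, screening procedures | serum test | no question |
| Table 1 and footnotes | tests at Visits 1, 2 and 3 | no item |
| Section 4.3, 8 reasons to end participation | reason 3 | not mentioned |

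**Count.** 12 + 24 = 36 listed criteria, of which none mentions breastfeeding, lactation or nursing. This 36 is a count of criteria; that it equals the planned number of randomized subjects is a coincidence.

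**Is text missing?** Both lists are numbered without a gap, 1 to 12 and 1 to 24, in the synopsis and in Section 4. Two complete copies lack the item, so this is not a fault of text extraction.

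**Does another provision cover it?**

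- A pregnancy test does not detect lactation, and a contraception requirement does not address it.
- Section 4.2 has no general item that lets the investigator refuse entry on judgement. The closest is reason 8 in Section 4.3. That concerns ending participation, not entry, and it refers to risk to the subject, not to an infant.
- Section 3.2.2 ties screen failure to Section 4 only: "A screen failure is defined as a subject who has signed the ICF, does not meet all the entry criteria outlined in" that section.
- Section 12.1 has the monitor record subjects enrolled without meeting all eligibility criteria. A woman who passes every listed item would not be caught by a check against the list.

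**Result.** Take a breastfeeding woman who otherwise qualifies, has negative serum and urine tests, and uses two contraceptive methods. She meets all 12 inclusion criteria and none of the 24 exclusion criteria. Under Section 4 she is eligible; under Section 7.6.1 she is excluded.

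**The case against.** The strongest reply is that Section 7.6.1 belongs to the same binding protocol and is categorical. Sections 10 and 11.2.2 require the study to be run as the protocol describes, and Section 4 does not say that no exclusion may stand elsewhere. On this reading, enrolling a breastfeeding woman would be a protocol deviation and not a permitted enrolment. An investigator who has read Section 7.6.1 would know of the exclusion. This stands in part: the exclusion is stated in the protocol, so the fault is a conflict between sections and not silence. It does not remove the problem, because the eligibility decision and the screen-failure definition both point to the numbered lists, and those lists pass her.

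Two further points stand. The eCRF and the consent form are not among the documents, so a breastfeeding question may already exist there. What can be shown is an omission from the criteria, not that any woman would actually be enrolled. Also, type 2 diabetes with steatosis above 8%, a liver stiffness of 6 to 12 kPa and two contraceptive methods make an eligible breastfeeding candidate improbable, though none of these rules her out.

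**Conclusion.** The concern holds. Section 7.6.1 states an exclusion that none of the 36 numbered criteria carries, and no screening procedure, schedule item or discontinuation reason makes up for it. A site that applies Section 4 as written can enrol a woman whom the protocol says is excluded.

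The number affected is probably very small. The documents give no figure for it, and that judgement is an inference from the other criteria. There is no effect on sample size, randomization, endpoints or analysis. The conclusion assumes that sites decide eligibility from the Section 4 lists, as Sections 3.2.2, 4.1 and 4.2 direct, and that no document outside those reviewed already carries the exclusion. It should be corrected because the inconsistency is certain, the remedy is simple, and the exposure is one the protocol says it prevents.

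**What to change.** Reconcile Section 7.6.1 with Sections 4.1 and 4.2 and the synopsis before enrolment. If the exclusion in Section 7.6.1 is what the sponsor intends, carry it into the numbered list in Section 4.2 and the synopsis, and add a matching eligibility item to the eCRF if none exists. If it is not intended, correct Section 7.6.1 so that it no longer claims a protection the criteria do not provide.

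Carrying the exclusion over costs one line in Section 4.2, one in the synopsis and one eligibility item on the eCRF. Neither option changes the sample size or the analysis.

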## 7.7 Adverse Event Severity Assessment

The Principal Investigator will provide an assessment of the severity of each adverse reaction by recording a severity rating on the appropriate AE reporting page of the subject's eCRF. Severity will be assessed according to the following scale:

*Mild* – events are usually transient and easily tolerated, requiring no special treatment and causing no disruption of the subject's normal daily activities.

*Moderate* – events introduce a low level of inconvenience or concern to the subject and may interfere with daily activities but are usually improved by simple therapeutic measures. Moderate experiences may cause some interference with functioning.

*Severe* – events interrupt the subject's normal daily activities and generally require systemic drug therapy or other treatment. They are usually incapacitating.

## 7.8 Expectedness of Adverse Event

An unexpected AE is defined in 21 CFR 312.32(a) as follows:

An AE is considered "unexpected" if it is not listed in the IB or is not listed at the specificity or severity that has been observed; or, if an IB is not required or available, is not consistent with the risk information described in the general investigational plan or elsewhere in the current application, as amended.

## 7.9 Assessment of Adverse Event Outcome

Outcome of AEs will be defined according to ICH Topic E2B, ICH Guideline.

- **Recovered/Resolved:** The subject has recovered fully from the AE without any remaining effects or impairment.
- **Recovered/Resolved with Sequelae:** The subject has recovered, but with an after effect possibly due to disease or treatment.
- **Not Recovered/Not Resolved:** The condition is still present.
- **Fatal:** Fatal should only be used when death is possibly related to the AE.
- **Unknown:** The primary outcome is not known at the time of the final assessment. If an outcome for an AE is not available at the time of the initial report, follow-up will proceed until an outcome is known or followed up to the Final Study Visit. Any subject with a possible IMP-related AE at the Final Study Visit will be followed until resolution or stabilization of the event. Further, any SAE, whether or not related to IMP (active or Placebo), that occurs within 30 days following the last dose of IMP will be followed until resolution or stabilization of the event.

## 7.10 Clinical Findings

Any significant clinical findings at Visit 9 will be followed until the condition returns to pre-study status, stabilizes, or can be explained as not being IMP related. If the clinical finding is reported as an AE (per the criteria outlined in [Section 7.2](#)), the follow-up procedures for AEs defined above will apply.

## 8 STATISTICAL METHODS

This section describes the statistical methods to be used for the analysis and reporting of data collected under Protocol No. ORA-D-N02. Additional details will be provided in the statistical analysis plan.

### 8.1 Sample Size

Up to 36 patients with NASH and Type 2 DM will be randomized to complete approximately 30 in this multi-center exploratory study. Subjects will be enrolled at 2 sites in Israel and 3 sites in the USA.

The treatment regimen will consist of a soft gelatin capsule containing 8 mg insulin, and 75 mg SBTI. Patients will take one capsule in the morning and one capsule at night, daily, or matching placebo, based on their randomized schedule.

The size of the study population was determined by reviewing the literature for pilot studies and was found to be sufficient to show trends of reducing liver fat content by MRI-PDFF images and CAP-Fibroscan. This study is not powered for statistical significance.

#### 8.1.1 Populations

**Safety Population:** All subjects who receive at least one dose of IMP will be included in the safety population.

**Intention to Treat:** All subjects who received treatment were included in the Intention to Treat population.

### 8.2 Safety Evaluation

#### 8.2.1 Adverse Events

AEs will be coded using the most current version of MedDRA. The severity of AEs will be graded according to NCI CTCAE version 4.03. AEs will be regarded as “pretreatment” if they occur during the Placebo Run-in Phase. TEAEs are defined as any AE that starts or increases in severity after the first dose of IMP at Visit 3.

The incidence of TEAEs will be tabulated by MedDRA preferred term, system organ class, treatment group, severity, and assigned relationship to IMP. The incidence for each TEAE will be provided as the total number of subjects that experienced the TEAE, as well as the percentage of the population that this represents. If a TEAE is reported more than once for a given subject, the greatest severity and the worst-case attribution will be presented in the summary tables.

TEAEs will be listed for individual subjects, along with information regarding onset and end dates, onset time where available, severity, seriousness, relationship to IMP, action taken, and outcome. A similar listing will be prepared for the pretreatment AEs.

Pretreatment AEs and TEAEs that lead to withdrawal from the study will be separately listed and summarized. Similarly, separate tabulations and listings will be prepared for pretreatment and treatment emergent SAEs.

Descriptive statistics will be generated as appropriate (i.e., frequency for categorical data). Inferential statistical analysis comparing the AE data between Active treatment and Placebo is not planned.

